Project Title: Preferred Method of Postoperative Follow Up After Pelvic Reconstructive Surgery. (Phone Call versus Clinic Visit): A Non-Inferiority Randomized Clinical Trial

Primary Investigator: [name]
Fellowship Program: University of South Florida
Year: PGY 6

Co-investigators:
[name], DO
[name]
[name]
[name]
[name]

I. Introduction:

Post-operative visits two weeks following reconstructive pelvic surgery is standard practice for our FPMRS division. With a growing number of new patients, scheduled procedures, and established patients, we, like most academic practices, struggle with maintaining an efficient workflow. To provide the best care, it is necessary to evaluate how we can improve patient satisfaction without seeing an increase in complications. Telephone consultations are increasingly being used as a novel approach to supplement or replace traditional outpatient care for various acute or chronic conditions. [1]. A review article published by Car, J and Sheikh, A found that telephone consultations are associated with increased patient satisfaction, less waiting time, and reduced travel costs. They also reviewed studies that both clinicians and patients value the convenience and flexibility offered by telephone consultations. However, amongst physicians dissatisfied with telephone -based care, the concerns cited included inability to confirm diagnosis with an examination and absence of visual cues [2]. Telephone follow up has been favorably evaluated following laparoscopic cholecystectomy, hernia repair, cardiovascular surgery, and

in oncology [2].

In the setting of urogynecological procedures, the use of telephone follow up is an area that needs to be studied. There is no known standardization about how postoperative follow up visits are conducted after pelvic reconstructive surgery. There is much variation amongst providers concerning when and how postoperative follow up visits are completed. With the advances in robotic and laparoscopic procedures, hospital length of stay has decreased significantly. We now must examine the benefits of minimally invasive surgery as it relates to postoperative follow up. If in person postoperative visits can be replaced with telephone visits, we can possibly increase patient satisfaction. By allowing the patient to have a postoperative visit in the comfort of her own home, we can save her travel costs and travel time. Additionally, in our practice, the in person postoperative visits can ultimately be replaced with procedures and established patient visits, ultimately allowing for more availability for new patient consultations. By evaluating the use of telephone follow up, versus clinic follow up we will show that patient satisfaction with telephone follow up will be unchanged or improved compared to our standard practices.

II. Objective:

A. Primary Aim(s):

- To determine if patient satisfaction with postoperative care with telephone follow up is non-inferior to clinic follow up.

B. Secondary Aim(s):

- To determine if telephone postoperative follow up is a safe alternative to clinic postoperative follow up visits
- To determine if telephone or clinic follow up visits are preferred based on differing demographics (i.e. age, race, distance traveled, outpatient versus inpatient surgery).
- To determine length of visit differences between telephone and clinic follow up.

III. Hypothesis:

For the standard two-week postoperative visit, follow up telephone calls will be non-inferior to traditional office visits. The telephone visit is a safe and efficient alternative to the in person visit following urogynecological procedures.

a. H_0 Traditional office visits are superior to follow up via telephone calls for two-week postoperative visits.

IV. Interventions:

Scheduled telephone call at the two-week postoperative visit completed by the urogynecology clinic nurse.

V. Study Design:

This is a two group, parallel randomized non-inferiority clinical trial at one institution evaluating telephone postoperative visits as non-inferior in patient satisfaction, patient preference, and patient safety, when compared with clinic postoperative visits. This protocol was written in accordance with CONSORT (Consolidated Standards of Reporting Trials) guidelines 2011.

VI: Methods:

A. Study Setting:

Patient recruitment will come from women presenting for their follow up clinic visit at the University of South Florida's (USF) Female Pelvic Medicine and Reconstructive Surgery (FPMRS) Clinic. Women who present to this follow up clinic visit have already been seen and evaluated within USF's FPMRS clinic by one of the FPMRS faculty, have undergone appropriate testing and are now receiving detailed, focused counseling in order to decide upon preferred surgical management. At this point a letter is sent to schedule the desired procedure. Once the physician and patient have agreed upon the surgical management plan it is the routine practice, at our institution, to submit a letter to the surgical scheduler. The letter details the type of surgery, medical clearance requests, and postoperative follow up. The patient is informed that she will be contacted, by our office, in the next two weeks and provided with all necessary information and documentation, including date of surgery and follow up appointments. It will be at this follow up clinic visit that patients will be told about our study and consented if applicable.

B. Eligibility:

The women that present to the USF FPMRS follow up visit and have decided to undergo surgical management of prolapse or incontinence, will be assessed to determine if they meet eligibility requirements. Eligibility requirements are as follows:

1. Inclusion Criteria:

- Women >18 desiring surgical management of prolapse or incontinence
- English speaking
- Willing and able to provide written and informed consent without assistance from medical surrogate or interpreter

- Immediate access to telephone services (landline, mobile phone, office phone)

2. Exclusion Criteria:

- Women <18
- Non-English speaking
- Unwilling and unable to provide written and informed consent without assistance from surrogate or interpreter
- Hearing impairment
- No access to telephone services (landline, mobile phone, office phone)
- Grade 3 complication- a complication requiring surgical, endoscopic, or radiological intervention. [3]
- Patient who did not attend any postoperative follow up visit

C. Interventions and Recruitment:

The recruitment and consenting process will be performed by an FPMRS fellow or an attending physician and will occur in a private patient exam room at the time of the surgical consultation follow up visit. After obtaining informed consent, the women will be randomized to either a two-week postoperative telephone visit or two-week postoperative clinic visit. The preferred contact phone number and mailing address will be confirmed. The patient will also receive a brief outline summarizing the study and what to expect in laymen terms. These visits typically occur during each of the three attending physicians' clinics. The provider will include that the patient is a study patient in the surgery letter. Once the surgical scheduler confirms that the patient has been enrolled and consented, she will open the next sealed randomization envelope revealing the patient's allocated intervention and schedule the patient's two-week postoperative visit accordingly (telephone follow up or clinic follow up). If the patient is randomized to telephone follow up, the surgical scheduler will again confirm the preferred contact number and mailing address.

Concerning the two-week postoperative follow up visit, if the patient is randomized into the telephone follow up group, she will be contacted, at the pre-scheduled date and time, by the urogynecology clinic nurse. The nurse will utilize a scripted series of postoperative questions, which are consistent with questions asked during our standard postoperative clinic visits. The same nurse will conduct the telephone follow up visits in an effort to maintain consistency. An example of the script is attached.

Any patient responses that are not consistent with a usual postoperative course will be escalated to an in person visit. However, these patients will remain in the group, to which they were originally randomized, for research analysis purposes. If a patient cannot be reached at the time of her scheduled telephone visit, a second

telephone call will be attempted during the same week. If there is still no answer, the patient will be scheduled for an in person visit, the time and date of this visit will be left on the patients voicemail. Patient will be excluded from study. Patients who were found to have recovered satisfactorily based on telephone follow up, will have six -week clinic visit.

Vital signs and physical examination will be deferred for the patients in the telephone follow up group. The clinic visit will entail questions about common postoperative complications (including fever, nausea/vomiting, pain, urinary symptoms, constipation, etc.). As per usual, vital signs and a focused physical examination will be completed at the clinic visit. All clinic visits will be performed by an FPRMS fellow and/or attending physician. At the end of each visit (telephone and clinic) patient will be reminded about postoperative restrictions as outlined in discharge instructions. The length of duration of both the telephone and clinic visits will be recorded by documenting the start and end time. For the clinic visit the start time will be the time patient is documented as “arrived” status in waiting area and finish time when the physician leaves the room. For the telephone visit, the start time will be at the time the patient answers the phone and finish time when phone call ends. Both clinic and telehealth visits will be documented with progress notes in EMR.

D. Randomization

Eligible patients will be randomized to Arm1 or Arm2 (Telephone follow up or clinic follow up). Permuted block randomization with randomly varying block sizes will be used. Generation of allocation sequences will be performed using a random-number table.

E. Concealment of Treatment Allocation:

The allocation sequence will be generated by our statistician who is neither responsible for patient recruitment or outcome assessment. Sequentially numbered opaque sealed envelopes will be used for concealment of treatment allocation.

F. Blinding:

It is not possible to mask clinical staff or participants, as they will be aware of the follow-up care that is being delivered over the telephone or in clinic. As such this is not a blinded study. The surgical scheduler will open the sealed randomization envelope revealing the patient’s allocated intervention and document this in the patients’ chart. The PI will keep the master link matching the patient to the allocated intervention. The PI is also responsible for entering all collected data into a de-identified excel spreadsheet.

VII. Outcomes

A. Primary:

- Comparison of patient satisfaction as determined by completion of a non-validated, treatment non-specific satisfaction questionnaire between the two groups. Survey will be provided at the six-week follow up visit.

B. Secondary:

- Comparison of adverse events and Emergency Department (ED) visits between the two groups. Will be determined by reviewing the patient's record to identify adverse events as defined below. Informed consent will include consent to obtain outside ED records; as this is standard practice for patients seen in ED during perioperative/postoperative period.
- Actual time spent on phone call during postoperative telephone follow up compared to time spent in clinic follow up measured in minutes.
- Correlation, between groups, of overall patient's satisfaction with subjective measures, complications, demographics, and travel distance.

VIII. Data Collection:

At the initial visit, once eligibility status is determined and consent is obtained, data collection form will include demographics, distance traveled, complications, and number of ED visits, type of surgery performed etc. Also patients will complete three postoperative patient satisfaction questionnaires at the six-week postoperative clinic visit. This will include the Patient Satisfaction Questionnaire (PSQ) 18 Short Form, a validated questionnaire. Also will include the Patient Global Impression of Improvement (PGII), a validated questionnaire. And a three-question survey about patient satisfaction with the postoperative experience, not validated. All six -week visits will be in person. The questionnaires will be completed before the physician interviews the patient. These questionnaires will be stored in a locked filing cabinet and later transferred by the PI to an excel spreadsheet stored on a password-protected computer. Additionally, pertinent medical information will be extracted from the patient's medical chart, de-identified, and transferred to the an excel spreadsheet after surgery by a member of the study team, including socio-demographic data, perioperative and postoperative details, adverse events, and ED visits.

Adverse events are defined based on previous studies [4, 5,]

- bladder injury
- ureteral injury
- bowel injury

- operative estimated blood loss >500mL
- reoperation < 30 days
- hematoma
- pelvic abscess
- vaginal cuff cellulitis
- ileus
- small bowel injury
- transfusion
- pulmonary
- cardiac
- neurological injury
- urinary tract infection (culture proven, urinalysis with presence of leukocyte esterase, nitrites, or blood, symptoms of infection)
- pyelonephritis
- urinary retention (more than 6 week postoperative)
- mesh erosion
- incisional hernia
- wound complication
- reoperation for complication of surgery
-

IX. Sample Size:

Sample sizes of 71 in Group 1 and 71 in Group 2 achieve 80% power to detect a non-inferiority margin difference between the group proportions of -0.12. The traditional office visit group proportion is 0.87. The Telehealth group proportion is assumed to be 0.75 under the null hypothesis of inferiority. The power was computed for the case when the actual Telehealth group proportion is 0.90. The test statistic used is the one-sided Z test (unpooled). The significance level of the test is 0.025.

X: Proposed Analyses:

Data analyses will be performed at the University of South Florida in Tampa, Fl. Data management and analyses will be conducted using SAS version 9.4 (SAS Institute, Inc, Cary, North Carolina). Subject demographic characteristics such as age, distance traveled, surgical procedures, ED visits will be summarized by standard descriptive statistics (e.g. means and standard deviations or median (range) for continuous variables and percentages for categorical variables. The difference between groups will be compared using the chi-square test or t-test, as appropriate. Logistic linear regression will be used to evaluate independent predictors for patient satisfaction. A p-value <0.05 will be considered statistically significant.

VIII. Confidentiality

At all times, appropriate measures will be taken to protect the confidentiality of all study participants in accordance with HIPAA guidelines. Patients will be approached for recruitment in private patient exam rooms. Once enrolled, all patients will be administered a study ID number starting with 1 and proceeding numerically. A master link between the individual subjects and their study ID number will be stored in a secure location (on a password-protected computer in the Urogynecology Fellows' office). All data collection forms (DCF) and stored patient information will only contain the study ID number. Charts will be reviewed in a secure location at all times. Upon completion of the data collection period, all information will be entered into an excel spreadsheet on a password-protected computer for data analysis.

IX Safety

This a voluntary study. Patients have the right to refuse to participate.

Data and Safety Monitoring

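### Section V claims non-inferior patient safety, but the plan sets no safety margin or confidence interval, offers only a difference test at 71 per arm, and removes some randomized patients from the comparison

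*Combined protocol and SAP*

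**What the plan says.** **The claim.** Section V (Study Design) says the trial is "evaluating telephone postoperative visits as non-inferior in patient satisfaction, patient preference, and patient safety, when compared with clinic postoperative visits". Section II.B lists as a secondary aim: "To determine if telephone postoperative follow up is a safe alternative to clinic postoperative follow up visits". Section III (Hypothesis) adds: "The telephone visit is a safe and efficient alternative to the in person visit following urogynecological procedures". The primary aim in Section II.A limits non-inferiority to satisfaction.

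**The outcome.** Section VII.B lists "Comparison of adverse events and Emergency Department (ED) visits between the two groups", identified by record review against the adverse-event list in Section VIII (Data Collection). That list includes reoperation.

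**The margin.** Section IX (Sample Size) says 71 per group "achieve 80% power to detect a non-inferiority margin difference between the group proportions of -0.12". It uses an office-visit proportion of 0.87, a telephone proportion of 0.75 under the null and 0.90 for power.

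**The analysis.** Section X says "The difference between groups will be compared using the chi-square test or t-test, as appropriate" and "A p-value <0.05 will be considered statistically significant". It mentions no confidence interval.

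**Who can leave after randomization.**
- The allocation envelope is opened when surgery is being scheduled (Section VI.C).
- The exclusion criteria in Section VI.B include "Grade 3 complication- a complication requiring surgical, endoscopic, or radiological intervention" and attending no postoperative visit.
- The Data and Safety Monitoring text describes exclusion criteria being met after surgery, including by women already allocated to telephone.
- Section VI.C excludes a telephone patient who is not reached on two attempts. It keeps patients escalated to an in-person visit in their randomized arm.

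**The concern.** A non-inferiority claim needs a stated margin and an interval, or a one-sided test, set against it. For safety the plan has neither. A difference test that fails to reach significance shows only that the data did not establish a difference. In a small trial that is compatible with a large excess of events. The plan offers no other route to the safety claim in Section V, and the claim matters because the telephone arm has no vital signs or examination at two weeks.

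The exclusions add a second problem. Reoperation is a listed adverse event and is also a complication needing surgical intervention. One event can therefore be a safety outcome and the reason the patient leaves the comparison. Exclusion for non-contact can occur in the telephone arm only.

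**Working it through.** **1. The plan's own sample size.** Inputs from Section IX: 0.87, 0.90, margin 0.12, one-sided alpha 0.025, power 80%, unpooled variance.

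n per arm = (1.960 + 0.842)² × (0.87×0.13 + 0.90×0.10) / (0.12 + 0.03)² = 7.849 × 0.2031 / 0.0225 = 70.8, rounded up to 71.

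The stated figure reproduces. A control proportion of 0.87 with 0.90 hoped for under telephone, where lower is worse, fits satisfaction. It cannot be an adverse-event rate, so the -0.12 margin does not carry over to safety.

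**2. Power of the planned difference test for safety.** The event rates are assumptions. Exact binomial enumeration, 71 per arm, uncorrected chi-square, two-sided 0.05:

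| Clinic rate | Telephone rate | Power | Missed |
|---|---|---|---|
| 5% | 10% | 21% | 79% |
| 10% | 20% | 39% | 61% |
| 20% | 30% | 29% | 71% |

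**3. How large an excess can be non-significant.** Take 7/71 (9.9%) in clinic and 15/71 (21.1%) by telephone.
- Difference = 8/71 = 11.3 points. Pooled rate = 22/142 = 0.155.
- z = 0.1127 / √(0.1549 × 0.8451 × 2/71) = 0.1127 / 0.0607 = 1.86, p = 0.064. One more telephone event (16/71) gives p = 0.040.
- Wilson limits: telephone 13.2% to 32.0%, clinic 4.9% to 19.0%.
- Newcombe lower limit = 11.3 - √(7.9² + 9.1²) = -0.8 points.
- Newcombe upper limit = 11.3 + √(10.8² + 5.0²) = +23.2 points.

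A result reported as not significant can thus be compatible with an excess of 23 points. Even identical counts of 7/71 in each arm leave an interval of ±10.4 points.

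**4. What a safety margin would require.** With a true rate of 10% in both arms (assumed), n per arm = 7.849 × 2 × 0.10 × 0.90 / margin² = 1.413 / margin². That gives 566 for 5 points, 142 for 10 points and 99 for 12 points. At 71 per arm, the chance that the Newcombe upper 95% limit falls below 5, 10 or 12 points is 15%, 48% or 62%.

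The answer depends on the rate. With a true rate of 3% in both arms, the chances for 10 and 12 points are 80% and 92%, although a 10-point margin would then accept 13% against 3%.

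**5. The exclusions.** These need reading rather than arithmetic.

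| Exclusion | Source | Arm affected |
|---|---|---|
| Grade 3 complication | VI.B; applied postoperatively in the Data and Safety Monitoring text | Both |
| No postoperative visit attended | VI.B | Both |
| Not reached by telephone | VI.C | Telephone only |

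All three are known only after allocation. Section VI.B gives no time limit for the Grade 3 exclusion. The monitoring text, which has an excluded telephone patient scheduled for a clinic visit, suggests that it acts mainly before the two-week contact. The documents give no frequency for any of the three, so no bias can be calculated.

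**The case against.** The strongest reply is that the conflict comes down to loose drafting in one sentence. Safety is a secondary aim, its outcome is only a comparison, and the trial is sized on other proportions. Section X plans percentages for categorical variables, so rates by arm, and intervals from them, could be reported from data already planned. Most of this stands, and it is why the main repair is to wording. But the aim and the hypothesis also call telephone follow-up safe, and no section supplies a decision rule. The nurse's script and the independent urologist's reviews protect patients but provide no inference.

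Three stronger readings are tempting, and the documents do not support them.
- *The investigators will read p>0.05 as proof of safety.* No section says so. The test sentence in Section X follows a list that names ED visits but not adverse events, so applying it to adverse events is itself an inference. If it does not apply, adverse events have no stated method at all.
- *The exclusions tilt the result toward telephone.* A complication before the two-week contact cannot be caused by how that contact is made, so dropping such patients need not favour either arm. Escalated patients are kept. Non-contact is a one-arm exclusion, but nothing shows whether those patients have more or fewer events.
- *No safety margin could ever be met with 71 per arm.* Step 4 shows that this fails at a low event rate with a wide margin.

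**Conclusion.** The concern holds. Section V claims non-inferior safety, and the plan has no safety margin, no interval and no analysis that could establish it. At 71 per arm, and at an assumed 10% clinic rate, the planned test misses a doubling about 61% of the time, and a non-significant result can be compatible with an excess of up to about 23 points. It cannot support the claim.

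The lack of a margin and interval is plain from the text and rests on no assumption. The percentages rest on assumed event rates. The post-randomization exclusions are a real secondary weakness in the safety comparison, of unknown size and direction. Because safety is a secondary aim and the remedy is mostly wording, this should be corrected but does not undermine the satisfaction comparison.

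**What to change.** 1. Remove patient safety from the non-inferiority claim in Section V, and reword the secondary aim (II.B) and the hypothesis (III) to match. State in Section X that adverse events and ED visits will be reported by arm as a risk difference with a score-based 95% confidence interval (Newcombe, for example), and that no conclusion of safety will be drawn from p>0.05. If the claim is to stay, the plan needs a justified safety margin and a sample size for it.
2. Keep all randomized patients who have surgery in the safety comparison, in their assigned arm, including those excluded for Grade 3 complications, non-contact or non-attendance, so far as consent allows.
3. Reconcile Section VI.B with the Data and Safety Monitoring text on when the Grade 3 exclusion applies.

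The cost is a few sentences of protocol text and slightly more chart review for the excluded patients. The sponsor must also accept a wide interval that this sample size cannot narrow, and give up the non-inferior safety claim.

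### A routine two-week examination in the clinic arm only can leave some adverse events unrecorded in the telephone arm, so the safety comparison can favour telephone follow-up

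*Combined protocol and SAP*

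**What the plan says.** Section VI.C describes two different two-week contacts.

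- **Clinic arm.** "As per usual, vital signs and a focused physical examination will be completed at the clinic visit". The assessor is a physician: "All clinic visits will be performed by an FPRMS fellow and/or attending physician".
- **Telephone arm.** "Vital signs and physical examination will be deferred for the patients in the telephone follow up group". A clinic nurse makes the call: "The nurse will utilize a scripted series of postoperative questions, which are consistent with questions asked during our standard postoperative clinic visits". There is a safeguard: "Any patient responses that are not consistent with a usual postoperative course will be escalated to an in person visit". Escalated patients stay in their randomized group for analysis.

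Both arms meet again later. Section VIII (Data Collection) states: "All six -week visits will be in person".

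Safety is a secondary aim (section II.B) and part of the hypothesis (section III). Section V also names it among the things on which telephone visits are to be shown non-inferior. The secondary outcome in section VII.B is "Comparison of adverse events and Emergency Department (ED) visits between the two groups", obtained by reviewing the patient's record, with outside ED records covered by the consent. The event list in section VIII (Data Collection) mixes intraoperative events, events that come to notice through symptoms or treatment, and events that a physical examination can show.

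Section X names a chi-square test or t-test for differences between groups. The documents do not mention recording how or when an event was detected, adjudication blind to arm, or a comparison limited to events found equally well in both arms. Section VI.F states that the trial is not blinded.

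**The concern.** A between-arm comparison of event counts is fair only if an event of a given kind has the same chance of entering the record in each arm. Here the chart holds a routine two-week examination for one arm only. At equal true risk, an event that only that examination would show is charted in the clinic arm and may never be charted in the telephone arm.

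The direction is what matters. The plan hopes to show that telephone follow-up is a safe alternative. Missing events in the experimental arm push towards that conclusion, and a real excess in the telephone arm could be partly hidden. A larger sample would not remove the error, because it is bias and not noise. That the visits differ by design explains the gap but does not make the two sets of chart records comparable.

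**Working it through.** **1. The plan's own figure.** The only sample-size calculation (section IX, Sample Size) concerns satisfaction. Its inputs are 0.87 for clinic, 0.90 for telephone, a margin of 0.12, one-sided alpha 0.025, 80% power and unpooled variance.

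n per arm = (1.960 + 0.842)² × (0.87×0.13 + 0.90×0.10) / (0.03 + 0.12)² = 7.85 × 0.2031 / 0.0225 ≈ 70.9, so 71. Power at 71 per arm is 80.1%. The figure reproduces. It says nothing about adverse events: the documents give no event rate, safety margin or safety sample size.

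**2. How an event reaches the record in each arm.**

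| Route | Clinic arm | Telephone arm |
|---|---|---|
| Symptom questions at two weeks | yes | yes (script) |
| Routine vital signs and examination at two weeks | yes | no |
| In-person visit after an abnormal answer | already in person | yes |
| ED visit, including outside records | yes | yes |
| In-person six-week visit | yes | yes |

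Only the second row differs in a way that matters. To be lost in the telephone arm alone, an event must (a) be visible on examination, (b) give no abnormal answer to the script, (c) lead to no other charted contact, and (d) be gone or not found at six weeks.

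**3. Which listed events can meet these conditions.** Hematoma, vaginal cuff cellulitis, wound complication and mesh erosion can be seen on examination, so mild or transient cases are candidates. Bladder, ureteral and bowel injury, blood loss, transfusion, reoperation and ED visits depend little or not at all on the two-week examination. Urinary retention is defined as lasting beyond six weeks, so it cannot be a two-week finding.

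**4. Size (every rate is an assumption).** Let p be the true risk, equal in both arms. Let s be the share of events that only the routine two-week examination would reveal; escalation is already allowed for in s. Let m be the fraction of those not found at six weeks. Take recording in the clinic arm as complete.

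Recorded telephone risk = p × (1 − s × m)

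| p | s | m | Telephone | Clinic | Difference (points) |
|---|---|---|---|---|---|
| 20% | any | 0 | 20% | 20% | 0 |
| 20% | 10% | 0.5 | 20% × 0.95 = 19% | 20% | −1 |
| 20% | 20% | 0.5 | 20% × 0.90 = 18% | 20% | −2 |
| 20% | 30% | 1 | 20% × 0.70 = 14% | 20% | −6 |

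With p from 10% to 30%, s from 10% to 30% and m from 0 to 1, the spurious difference runs from 0 to −9 points. The last value is 30% × 0.30 × 1. The sign follows from the mechanism: it can be zero but cannot favour the clinic arm.

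Read the other way, if both arms record 20% with s = 30% and m = 1, the true telephone risk is 20% / 0.70 = 28.6%, a hidden excess of 8.6 points.

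**5. Scale.** At 71 per arm and 20% risk, the 95% half-width for a difference is 1.96 × √(2 × 0.20 × 0.80 / 71) = 13.2 points. At 20% risk the bias (up to 6 points) is smaller than the sampling error, but it always pushes the same way.

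**The case against.** The strongest reply is that the plan already closes most of the gap. The script follows the questions asked in clinic, abnormal answers bring the patient in, outside ED records are sought without distinction by arm, and everyone is seen in person at six weeks. Many listed events do not depend on a two-week examination at all. This stands, and it limits the problem to the four conditions in step 2 of the working.

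Four stronger readings are tempting, and the documents do not support them.

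- *That only clinic patients are examined at two weeks.* This is true of the routine examination only; escalated telephone patients are also seen in person.
- *That the comparison necessarily makes telephone look safer.* If everything missed at two weeks is found at six weeks, the bias is zero. The right verb is can.
- *That urinary infection is an example.* The definition includes "urinalysis with presence of leukocyte esterase, nitrites, or blood, symptoms of infection", but nothing says a urinalysis is done at the clinic visit, and a physical examination does not supply one.
- *That the examination inflates the clinic rate above the truth.* If the findings are real events, the clinic record is at most the true rate. The error is under-recording in the telephone arm.

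It may also be said that section X does not name adverse events next to the chi-square and t-test; that sentence follows a list of subject characteristics and ED visits. That is so, but no other method is stated for the between-group comparison promised in section VII.B.

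Finally, if an early finding is missed and leads to a later, worse event, that is a real effect of telephone follow-up, not detection bias, and should be counted.

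**Conclusion.** The point holds in a limited form. The plan provides unequal routine ascertainment at two weeks, takes events from the chart, and states no step to make the comparison fair. Mild or transient events visible on examination can therefore go unrecorded in the telephone arm, in the direction that favours the plan's safety aim.

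The size cannot be derived from the documents. Under the assumptions shown (true risk 20%, s of 10–30%, m of 50–100%), the telephone arm would record about 14–19% against 20%. This takes clinic-arm recording as complete and the six-week visit as conducted alike in both arms; the documents do not describe the content of that visit. The primary satisfaction outcome and its sample size are unaffected.

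**What to change.** Clinical care need not change.

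1. Add to the chart abstraction the date and route of first detection of each event: routine two-week examination, escalated visit, ED or other unscheduled contact, or six-week visit.
2. Make the main between-arm safety comparison on outcomes that do not depend on the two-week examination: ED visits including outside records, transfusion, and findings present at the six-week in-person visit.
3. Include reoperation in that comparison only if patients excluded postoperatively for a Grade 3 complication (section VI.B; Data and Safety Monitoring) are kept in the safety set, and state this. Otherwise the exclusion removes many of the reoperations to be counted.
4. Do not widen the six-week item to events treated by six weeks. That would readmit events found and treated at the two-week clinic examination, and the bias with them.
5. Tabulate events first found at the routine two-week examination separately. Show the all-event comparison as secondary, labelled as subject to unequal ascertainment.

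This is a cheap improvement. It costs one more abstraction field and some added text in the analysis section. The downside is fewer events, and so less precision, in the main safety comparison.
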